We will test an artificial intelligence-based Risk Map DSS tool we have developed, which is based on and expanded from previously identified key MR image features that are effective for identifying PCa from normal prostate tissue, and which also correlates moderately with Gleason scores (ADC, T2, and tissue composition maps). The DSS tool will assist radiologists interrogate suspicious areas in the prostate that are potentially clinically significant PCa foci, and will identify up to two potential clinically significant tumor sites. In addition to systematic biopsies and the targets identified by the radiologist, up to two targets determined by the DSS tool will be biopsied. Biopsy histology results of all cores will be used as the reference standard to evaluate the performance of the Risk Map DSS tool.

C. METHODOLOGY

C.1. Study Design:

This is a prospective, single-arm, unblinded study of patients with known or suspected prostate cancer. A total of 125 patients will be enrolled.

Recruitment: We will recruit patients with known or suspected prostate cancer who have been referred to the Department of Radiology at the University of Chicago Medical Center for a diagnostic MRI exam of the prostate, to be followed by an MRI-guided fusion biopsy of the prostate, per standard clinical protocol.

All patients will be scanned using a standard clinical prostate MRI protocol. Research sequences will be added to the routine clinical exam. The research sequences will not exceed 15 minutes. The patients will not receive intravenous contrast agent as part of the research protocol.

All patients will then undergo a 12-core TRUS-guided or transperineal US-guided sextant random biopsy by their urologist at the Urology Clinic as their standard of care treatment. Additional biopsy targets may be selected based on an expert radiologist's interpretation of the patient's clinical MRI, as part of the clinical, standard of care MR targeted biopsy procedure. Up to two additional biopsy targets per patient will be selected by the Risk

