Map DSS tool, if different from the already selected targets by the radiologist per standard of care. Ultimately, the clinical radiologist will make the final decision on the targets to be biopsied. MR-targeted biopsies will be done by using a Uronav MR-US fusion device. The following results will be recorded for each core: (1) the reason of biopsy (random biopsy; DSS tool alone; radiologist alone) (2) location (sextant and zone), and (2) histology result. Research cores will be evaluated by expert genitourinary pathologist, [name], and results will be communicated to the urologist.

Studies will be carried out using FDA approved 3 Tesla Philips, GE and Siemens MRI units at the University of Chicago Medical Center. All of the research MR sequences will be in compliance with FDA safety requirements and MR contrast agents will not be injected for research purposes.

C.2. MRI Data acquisition methods:

The data acquisition will consist of obtaining the standard clinical protocol and research sequences, in compliance with FDA safety requirements. Research sequences may include, but will not be limited to (1) KT-T2 sequence (high spatial resolution axial ME-TSE for T₂ measurements and anatomy visualization), and (2) axial HM-MRI with 4 b-values and 4 TEs for diffusion and T2 measurements. MR images will be acquired using Philips, GE or Siemens 3T clinical MR systems with a phased array surface receiver coil.

C.3. Study Endpoints and Statistical Analysis

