The major goal of this study is to compare the accuracy of the Risk Map DSS tool against the clinical accuracy of experienced radiologists in the context of the reference standard of biopsy histology. The primary endpoints will be ROC curve, AUC value, the secondary endpoint will be sensitivity, specificity, PPV, and NPV, and the tertiary endpoint will be correlation strength between the DSS tool output and tumor-specific Gleason scores. Both per-patient and per-tumor analyses will be conducted. For the per-patient analysis, patients who are diagnosed with PCa from the biopsy procedure will be considered as positive for PCa, and patients who are not diagnosed with PCa from the biopsy procedure will be considered as negative for PCa. For the per-tumor analysis, each individual PCa tumor diagnosed from the biopsy procedure will be analyzed separately, and biopsy sites that do not yield PCa diagnosis will be considered as negative for PCa. To ascertain a true positive biopsy, the finding and the biopsy must match in sextant and zone. If ambiguity in biopsy site arises with regard to indications from the DSS tool, or the radiologist's opinion, and the biopsy, expert radiologist ([name]) and pathologist ([name]) will review each case to make the determination. This will allow us to calculate the performance of: (1) the Risk Map DSS tool, (2) the radiologist, and (2) the standard sextant biopsy. We will evaluate these performance endpoints on clinically significant PCa (but we will have data for all tumors). Spearman correlation coefficient will be estimated in the usual manner.

C.4. Statistical power consideration

We expect the following level of performance: AUC 0.90±0.03, sensitivity 90±5%, specificity 90±4%, and statistically significant (Spearman's) correlation strength of 0.8 with tumor-specific Gleason scores. Variances are estimated based on the expectation of PCa diagnosis in 35% of 125 patients, and based on an empirical rule-of-thumb formula

for AUC and binomial probability for sensitivity and specificity. The estimated 95% confidence intervals (CIs) are: for AUC [0.87, 0.93], for sensitivity [0.85, 0.95], and for specificity [0.86, 0.94]. These uncertainty estimates do not include analysis of biopsy by sextant and zone of the 12-20 cores per patient; estimates of 12 by-location-analyses per patient reduce all uncertainties to about 1%. These estimates suggest that this protocol will produce meaningful performance estimates.

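### Per-tumor sensitivity and specificity use biopsied sites only, and a sextant-zone location without a systematic core is biopsied only if the DSS or the radiologist flagged it

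*Combined protocol and SAP*

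**What the plan says.** **Matching and negatives (C.3).** The site-level rule is: "To ascertain a true positive biopsy, the finding and the biopsy must match in sextant and zone". On the negative side, "biopsy sites that do not yield PCa diagnosis will be considered as negative for PCa". A location with no core is therefore neither positive nor negative and leaves the analysis.

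**Sampling that does not depend on the tests (C.1).** "All patients will then undergo a 12-core TRUS-guided or transperineal US-guided sextant random biopsy by their urologist". Cores are described by sextant; nothing allocates them to zones.

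**Sampling that does depend on the tests (C.1).** "Additional biopsy targets may be selected based on an expert radiologist's interpretation of the patient's clinical MRI". Up to two further targets come from the Risk "Map DSS tool, if different from the already selected targets by the radiologist per standard of care". Then: "Ultimately, the clinical radiologist will make the final decision on the targets to be biopsied". C.4 expects 12 to 20 cores per patient, so up to 8 beyond the systematic 12. For each core the study records its sextant and zone, its histology, and "the reason of biopsy (random biopsy; DSS tool alone; radiologist alone").

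**Claimed precision (C.4).** "estimates of 12 by-location-analyses per patient reduce all uncertainties to about 1" percent.

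The protocol does not list the zones used for matching. It gives no rule for locations without a core, no restriction of accuracy to systematically sampled locations, and no correction for verification bias.

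**The concern.** In a sextant-zone location without a systematic core, histology exists only if one of the two tests under evaluation pointed there. A tumor that both miss cannot appear as a false negative, and a benign location that both correctly leave alone cannot appear as a true negative. Flagged locations are therefore over-represented among both cancers and non-cancers. That raises apparent sensitivity and lowers apparent specificity, even if every DSS target is biopsied. These are secondary endpoints, but C.4 credits the by-location analysis with about 1% uncertainty. A bias of a few points would exceed that and would not shrink with more patients.

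**Working it through.** **1. The plan's own figure.** Inputs from C.4: 125 patients, 35% positive, sensitivity and specificity 90%, AUC 0.90.
- Positives: 0.35 × 125 = 43.75. Negatives: 81.25.
- Patient-level SE: sensitivity √(0.09/43.75) = 0.045; specificity √(0.09/81.25) = 0.033; AUC (Hanley–McNeil) 0.033.
- With 12 locations per patient: √(0.09/525) = 0.013; √(0.09/975) = 0.0096; AUC 0.0095.

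So about 1% reproduces, but only for 1,500 independent locations that all have histology.

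**2. Coverage.** Twelve cores can reach at most 12 cells.
- 6 sextants × 2 zones = 12 cells: complete only if each cell receives exactly one core.
- 18 sectors, as in the preliminary risk-map study (A.3.2): at most 12/18 = 67% covered.
- 6 × 4 = 24 cells, using the four regions of A.3.1: at most 50% covered. This assumes that all four regions occur in every sextant, which the protocol does not say.

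The share f of uncovered cells is therefore an assumption; 25% and 50% are used below.

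**3. Expected bias.** Assume both tools have sensitivity se and specificity sp, cores are read without error, and every flagged uncovered cell is biopsied. Let v+ and v− be the probabilities that at least one tool flags a cancer cell or a benign cell.
- Apparent sensitivity = se / [(1 − f) + f·v+]
- Apparent specificity = [(1 − f)·sp + f·(v− − (1 − sp))] / [(1 − f) + f·v−]
- Independent tools: v+ = 1 − 0.1² = 0.99; v− = 1 − 0.9² = 0.19. Identical flags: v+ = 0.90; v− = 0.10.

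| f | Tools | Sensitivity | Specificity |
|---|---|---|---|
| 50% | independent | 0.9/0.995 = 90.5% | 0.495/0.595 = 83.2% |
| 50% | identical | 0.9/0.95 = 94.7% | 0.45/0.55 = 81.8% |
| 25% | independent | 0.9/0.9975 = 90.2% | 0.6975/0.7975 = 87.5% |
| 25% | identical | 0.9/0.975 = 92.3% | 0.675/0.775 = 87.1% |

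**4. Variations.** Half the cells covered, 10% cell prevalence, radiologist at an assumed 80%/90%, correlation between the tools 0 or 0.5, systematic-core miss rate 0 or 30%:
- No DSS-only target declined: sensitivity 90.9–93.1%, specificity 82.9–83.2%.
- Half declined: 90.5–92.8% and 85.2–86.5%.
- All declined: 90.0–92.4% and 87.6–90.0%.

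No scenario with incomplete coverage put sensitivity below 90% or specificity above 90%. The fall in specificity comes from the biopsied-sites rule. If unsampled cells were counted negative instead (half the cells covered, identical flags), specificity would stay at about 90%, but sensitivity would still read 94.7%.

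**5. AUC.** A binormal simulation set the true AUC at 0.90, with flags raised at the 90%-specificity threshold. AUC was 0.901 with full coverage, and 0.904 and 0.903 with 67% and 50% of unflagged sites sampled.

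**6. Candidate fixes.** Over locations with a systematic core, inclusion does not depend on the flags, so the formulas with f = 0 return 90%/90% when cores are read without error.

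Making the sextant the unit does not achieve this. Take two cells per sextant with one sampled, 10% cell prevalence, and the 75%/89% of A.3.2. True sextant sensitivity is 79% and specificity 0.89² = 79%.
- If all cores count, sensitivity reads 81% (independent) to 88% (identical).
- If flagged-only cells are dropped from the reference, a cell is flagged with probability 0.1 × 0.75 + 0.9 × 0.11 = 0.174, and specificity reads 0.89 × (1 − 0.174) = 73.5%.

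**The case against.** The best reply is that C.4's 12 locations per patient equal the 12 systematic cores. If these are six sextants by two zones with one core in each, every cell has histology and the bias is nil. That is right, but the protocol does not say so, and a random sextant biopsy does not ensure it.

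It can also be said that C.3 uses sextant and zone to attribute a finding to a core, not to define a grid, and that the 24-cell count borrows regions from a preliminary figure. Both are fair, and they leave f unknown. They do not remove the selection, because the denominators are still the biopsied sites.

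The model in step 3 biopsies every flagged uncovered cell, whereas the DSS may add at most two targets and the radiologist may decline them. Declining targets shrank the bias in step 4 without reversing it. With independent tools the gain in sensitivity is only about half a point, so most of the effect is then on specificity.

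Three stronger readings are tempting, and the documents do not support them:
- **Uncovered zones show near-perfect sensitivity by construction.** At f = 100% the formulas give 0.9/0.99 = 90.9% sensitivity and 0.09/0.19 = 47% specificity for independent tools. The extreme of 100% and 0% needs both tools to flag exactly the same cells, and nothing in the plan says they will.
- **The primary AUC is materially distorted.** It moved by 0.003 at most in the simulation.
- **The per-patient results are affected in the same way.** Every patient is biopsied, so this cell-level selection is absent there.

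**Conclusion.** The point holds for per-tumor sensitivity and specificity. As C.3 is written, a location without a systematic core enters those estimates only if a test under evaluation selected it, and nothing in the plan corrects for this. Where coverage is incomplete, the expected bias is upward for sensitivity and downward for specificity.

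The size cannot be determined from the documents. At 90%/90% and f between 25% and 50%, it is +0.2 to +4.7 points for sensitivity and about −3 to −8 points for specificity. This assumes error-free cores and biopsy of every flagged uncovered cell; declined targets make it smaller. It is zero if the 12 cores fill every cell. Specificity in particular could be off by several times the 1% uncertainty in C.4. This should be corrected before analysis, but it does not undermine the per-patient analysis or, on the evidence of one simulation, the AUC.

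**What to change.** In C.3:
- List the zones used for matching, and state how the 12 systematic cores are distributed over the sextant-zone cells.
- Compute site-level sensitivity, specificity and NPV, for the DSS and for the radiologist, only over sextant-zone locations that received a systematic core. Identify these from the recorded reason and location of each core.
- Report locations sampled only because a tool flagged them in a separate detection-yield and PPV table, outside those denominators.
- Give the all-cores estimate as a secondary analysis, labelled as subject to verification bias.
- State whether a targeted core in an eligible location counts toward its reference. With complete coverage, no declined targets and a 30% systematic-core miss rate, counting it still gave an apparent sensitivity of 90.5–91.4% against a true 90%.

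Do not adopt the sextant as the unit to cure this: a tumor in an unsampled, unflagged zone would then count as a true negative.

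The cost is analysis wording only; C.1 already records what is needed, and no biopsy procedure changes. The price is fewer sites in the site-level analysis, and no accuracy estimate for zones that the systematic cores do not reach.

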Protection against risks related to presence of metals, devices and other metal containing material: Participants are questioned carefully before MRI imaging to insure that they do not have metal implants. Prospective study participants who have such implants will be excluded from the study. Patients who have worked in or near machine shops and electronics shops and may have had metal slivers become trapped in their eyes, posing a potential hazard if exposed to a strong magnetic field, will also be excluded from the study. In addition, metal objects such as heavy key chains that are carried into the scan room can cause serious accidents. Participants will be cautioned to remove all metal objects before entering the scan room. Access to the scan room is carefully controlled to insure that no ferrous metal is inadvertently brought in.

Protection against claustrophobia: Prospective participants will be counseled about this possibility before the exam. The magnet is equipped with an intercom system enabling study subjects to communicate with the operators at any time during the exam. If they report any discomfort during the MRI examination they will be removed from the magnet immediately.

Protection against the breach of confidentiality: Patient identifiers will be kept and used only for the purpose of correlating patient data between radiology, urology and pathology. Patient identifiers will be removed from data analysis unless it becomes necessary to correlate results of the analysis to other clinical data, which we do not expect. Patient identifiers will be removed from all presentations and publications; only data from a group of patients will be reported so that data from any individual patient cannot be identified.

Risks associated with Transrectal and Transperineal Ultrasound-Guided Prostate Biopsy:

The risks will be those associated with standard MRI-guided fusion biopsy of the prostate, which the patients will undergo for clinical indications. The research component (upto two additional biopsy targets) will cause a minimal increase in the risk of bleeding and infection.

Benefits

There may or may not be any direct medical benefit to patients who are enrolled in the study.

There will be a long-term benefit to society in general if this research leads to the development of a new technology that improves clinical practice.

Alternatives

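### Ambiguous site matches are adjudicated with no masking of tool or histology, and a pathology reader is named only for research cores, so labelling that differs by tool is not prevented

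*Combined protocol and SAP*

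**What the plan says.** Section C.1 describes the design: "This is a prospective, single-arm, unblinded study of patients with known or suspected prostate cancer". Section B sets the reference: "Biopsy histology results of all cores will be used as the reference standard".

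For each core, C.1 has the study record "the reason of biopsy (random biopsy; DSS tool alone; radiologist alone", together with location and histology. On reading, C.1 states: "Research cores will be evaluated by expert genitourinary pathologist". Section K identifies what is research in the biopsy: "The research component (upto two additional biopsy targets". In C.1 these are the targets chosen by the DSS tool. Radiologist targets are taken "as part of the clinical, standard of care MR targeted biopsy procedure", and the 12-core sampling is also standard care. No reader is given for either of those two groups.

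Section C.3 gives the matching rule: "To ascertain a true positive biopsy, the finding and the biopsy must match in sextant and zone". If the site is ambiguous in relation to the DSS indication, the radiologist's opinion and the biopsy, an "expert radiologist ([name]) and pathologist ([name]) will review each case to make the determination".

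No section masks the pathologist to the source of a core, or masks the adjudicators to the tool or the histology.

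**The concern.** The stated major goal in C.3 is to compare the DSS tool with experienced radiologists, using biopsy histology as the truth. Two judgements supply the labels for that comparison: the grade given to each core, and the decision whether a mark and a core refer to the same place. If either can be made with knowledge of which tool is being scored, errors need not fall equally on the two tools. More patients would not remove a bias of that kind.

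The matching judgement is the clearer problem, because the procedure as written puts the tool's mark in front of the adjudicators and hides nothing else from them. The grading judgement matters because C.3 evaluates the endpoints on clinically significant cancer. The background section defines that mainly by a Gleason score above 6, so a reader's placing of that boundary affects which cores count. The tertiary Gleason correlation uses the same grades.

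The investigators developed the DSS tool (section B), and the tissue-composition work that feeds it led to a patent application (A.3.1). This implies nothing improper, but it is an ordinary reason to mask judgement calls.

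**Working it through.** **Step 1. Matching.** Four elements of the plan, side by side:

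- Default: an agreement rule on sextant and zone (C.3).
- Exception: expert review when the site is ambiguous (C.3).
- Question at review: how the biopsy site relates to the DSS indication or the radiologist's opinion (C.3).
- Masking: none stated, in a study called unblinded (C.1).

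Followed as written, the review can take place with the tool known and the histology available.

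**Step 2. Reading.** C.1 assigns research cores to one expert genitourinary pathologist. Section K and C.1 together make the research cores the DSS targets, at most two per patient. The reader of the random and radiologist-targeted cores is not given. Nothing guarantees one reader across sources, and if the routing is separate, it could itself reveal the source of a research core.

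**Step 3. Scale.** No figure in the plan bears directly on masking. The nearest yardstick is the C.4 sensitivity of 90±5%.

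- Positive patients: 0.35 × 125 = 43.75, about 44.
- Binomial SE: √(0.90 × 0.10 / 43.75) = 0.0454, or 4.5 points. This is about the plan's ±5, so that figure is roughly one SE, although C.4 presents [0.85, 0.95] as a 95% interval.
- 95% half-width: 1.96 × 4.54 = 8.9 points.
- One patient reassigned: 1/44 = 0.0227, or 2.3 points of per-patient sensitivity.

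The documents give neither the share of positive patients with an ambiguous match (*a*) nor the net share of those settled in one direction (*f*). Both are assumed. Shift = 100 × *a* × *f* points:

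| *a* | *f* = 25% | *f* = 50% | *f* = 100% |
|---|---|---|---|
| 5% | 1.25 | 2.5 | 5 |
| 10% | 2.5 | 5 | 10 |
| 20% | 5 | 10 | 20 |

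In patients, this runs from 44 × 0.05 × 0.25 = 0.6 to 44 × 0.20 × 1.00 = 8.8. From a sensitivity of 90%, an upward shift cannot exceed 100 − 90 = 10 points, so the upper end of the range could only be a loss for the tool concerned.

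**Limits of this arithmetic.** The 44 counts patients with any PCa, not lesions and not clinically significant cancers. The per-tumor denominator is not given. The calculation also assumes that the location rule applies to a true positive in the per-patient analysis, which C.3 does not spell out. AUC is the primary endpoint, but C.3 does not say how location matches enter the ROC curve, so no shift in AUC is computed.

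**The case against.** The strongest reply is that silence on masking is not a documented unmasked read. The word unblinded describes the study as a whole. Recording the reason for biopsy does not mean that the pathologist sees it. The default match is a rule rather than an opinion, and review is the exception. Patient disease status comes from the biopsy diagnosis, so site adjudication cannot change who is positive. One pathologist may already read every core.

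Much of that stands, and it rules out several stronger readings that a reader might infer:

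- **That histology is read with the source in view.** No section says so. It is only not prevented.
- **That a different pathologist grades the other cores.** The reader of those cores is unstated, and names are removed from the text.
- **That matches are settled after the histology is known.** C.3 gives no timing. It only fails to withhold the result.
- **That the adjudicating radiologist is the one being scored.** The text does not show any overlap.
- **That each adjudicated lesion is worth 2.3 points.** The 44 is a count of patients.

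The reply does not dispose of the adjudication step. C.3 describes a procedure, and that procedure includes the tool's mark and no masking. A fixed default rule does not protect the cases that fall outside it, and those are the cases in which judgement decides whether a mark counts.

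**Conclusion.** The concern holds in a limited form. For ambiguous sites, the plan lets a radiologist and a pathologist decide matches with no masking of tool or histology. It names an expert reader for the DSS cores alone and leaves the reader of the rest unstated. Differential labelling by tool is therefore possible and not guarded against; the documents do not show that it occurs.

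The size cannot be fixed from the documents. Under the assumed ranges, the shift in per-patient sensitivity is about 1 to 20 points. The middle case (10% ambiguous, net 50% one way) gives 5 points, about the size of the plan's own ±5. At the low end the effect is minor. The number of ambiguous cases and the direction of their resolution are assumptions throughout. The case for acting is that the protection is cheap and the exposed step feeds the study's main comparison.

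**What to change.** **In C.3**, state that ambiguous matches are decided from location data alone (sextant, zone and fusion coordinates), with tool identity and histology hidden, and that each decision is recorded before unmasking.

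**In C.1**, state that cores are submitted under coded identifiers with location, and that the reason for biopsy is held in the study database. The code is needed because location alone would not separate a random core from a targeted core at the same site, and the analysis depends on that link. Where existing workflow allows, have the same genitourinary pathologist read all of a patient's cores. In any case, state who reads the cores that are not research cores.

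**Cost.** Minor preparation of coded cases and labels, and a few sentences of protocol text. No second read is required. If the site already works this way, only the text needs to change. If the adjudicating pathologist also read the cores, coding reduces recall of the result but may not remove it, and the report should say so.

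### Sextant biopsy is scored against a reference that includes its own 12 cores, so per patient its specificity and PPV are fixed at 100%; the DSS-versus-radiologist goal has no stated difference estimate or precision

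*Combined protocol and SAP*

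**What the plan says.** **Reference standard.** Section B states: "Biopsy histology results of all cores will be used as the reference standard to evaluate the performance of the Risk Map DSS tool". Section C.1 gives every patient a 12-core systematic biopsy, so those cores are part of the reference. Section C.3 sets the per-patient rule: "patients who are diagnosed with PCa from the biopsy procedure will be considered as positive for PCa". Sites without a cancer diagnosis count as negative.

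**Methods scored.** C.3 continues: "This will allow us to calculate the performance of: (1) the Risk Map DSS tool, (2) the radiologist, and (2) the standard sextant biopsy". The next sentence reads: "We will evaluate these performance endpoints on clinically significant PCa". The endpoints named in C.3 are the ROC curve and AUC (primary), then sensitivity, specificity, PPV and NPV (secondary), then correlation with Gleason score. Nowhere are the sextant cores removed from the reference when sextant biopsy is the method being scored.

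**Core labels.** C.1 records for each core "the reason of biopsy (random biopsy; DSS tool alone; radiologist alone", together with its sextant and zone. There is no label for a target chosen by both the tool and the radiologist.

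**Main comparison.** C.3 opens: "The major goal of this study is to compare the accuracy of the Risk Map DSS tool against the clinical accuracy of experienced radiologists". It names no difference measure, no paired method and no interval for a difference.

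**Precision.** C.4 says: "Variances are estimated based on the expectation of PCa diagnosis in 35% of 125 patients". It gives one set of expected values: AUC 0.90±0.03, sensitivity 90±5% and specificity 90±4%. The AUC interval is stated as "The estimated 95% confidence intervals (CIs) are: for AUC [0.87, 0.93". It gives no radiologist AUC and no correlation between the two readings.

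**The concern.** A test cannot be wrong in the positive direction against a reference that its own positive result creates. A three-method table would set a sextant specificity and PPV that cannot fall below 100% beside DSS and radiologist figures that can. A reader would take the 100% as a finding about sextant biopsy when it follows from the scoring rule.

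The second matter is a gap. The study exists to compare two readings of the same patients, but the plan does not say what number expresses that comparison or how precisely it will be known. Precision for one method does not answer this. The precision of a paired difference also depends on the radiologist's AUC and on how strongly the two AUC estimates are correlated.

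**Working it through.** **1. Sextant biopsy, per patient, same threshold for test and reference**

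Let S mean that at least one sextant core is positive and T that at least one targeted core is positive. The reference is R = S or T.

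- False positives: S positive and R negative. This is impossible, so FP = 0.
- Specificity = TN/(TN + 0) = 100%. PPV = TP/(TP + 0) = 100%.
- One-point AUC = (sensitivity + specificity)/2 = (1 + sensitivity)/2. For example, sensitivity 0.6 gives 0.80.
- NPV can vary. At C.4's 35% of 125 (43.75 positive, 81.25 negative), sensitivity 0.6 gives 81.25/(81.25 + 0.4 × 43.75) = 0.82.

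A simulation gave specificity and PPV of exactly 1.000 in every scenario, including one with 5% false-positive cores.

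Sensitivity is relative to what the cores jointly found. Suppose the 12 cores find a share s of true cancers, targeted cores find a share t of the rest, and no core is falsely positive. Reported sensitivity is then s/(s + (1 − s)t). With assumed s = 0.6, t = 0.5 gives 0.6/0.8 = 0.75, and t = 0.9 gives 0.6/0.96 = 0.63.

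Two conditions matter:

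- *Threshold.* If sextant biopsy were called positive for any cancer against a reference of clinically significant cancer, false positives could occur. C.3 uses both terms.
- *Location.* Per location, FP = 0 needs the status of a sextant and zone to be the composite of all cores in it. If each core were its own site, a negative targeted core beside a positive sextant core could count as a false positive. The protocol does not settle this.

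**2. The plan's own precision figures**

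Hanley-McNeil with A = 0.90, m = 43.75 and n = 81.25:

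- Q1 = A/(2 − A) = 0.8182; Q2 = 2A²/(1 + A) = 0.8526; A² = 0.81.
- SE² = [A(1 − A) + (m − 1)(Q1 − A²) + (n − 1)(Q2 − A²)]/(mn) = (0.090 + 0.350 + 3.421)/3554.7 = 0.001086, so SE = 0.0330.
- 95% half-width = 1.96 × 0.0330 = 0.065, or 0.84 to 0.96.

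The simpler √(A(1 − A)/125) gives SE = 0.027. C.4 does not name its rule of thumb. On either formula, its ±0.03 is about one SE, and the interval labelled 95% is about ±1 SE.

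**3. Precision of the paired AUC difference**

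SE_d = √(SE₁² + SE₂² − 2r·SE₁·SE₂); half-width = 1.96 × SE_d. Assumed, because the documents give no values: radiologist AUC 0.82 to 0.90 and correlation r between the AUC estimates 0.3 to 0.6. The DSS AUC is set at 0.90. The Hanley-McNeil SE at AUC 0.82 is 0.0426.

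| Radiologist AUC | r = 0.6 | r = 0.3 |
|---|---|---|
| 0.90 | 0.058 | 0.076 |
| 0.82 | 0.068 | 0.089 |

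A simulated DeLong analysis with binormal scores (44 positive, 81 negative) gave 0.05 to 0.08 for the same settings. The 35% is an expectation. At 20% positive the Hanley-McNeil range is 0.074 to 0.113, and at 50% it is 0.050 to 0.079. The per-location analysis is not sized here.

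**The case against.** Several points on the other side have force.

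- *Intent.* Section B's all-cores sentence is written for the DSS tool, and C.3 does not say outright that specificity, PPV or AUC will be tabulated for sextant biopsy. This stands as an ambiguity. However, C.3's patient-level rule is general, no other reference is offered, and the sentence after the list of methods applies the performance endpoints without exempting any method.
- *Per-tumor analysis.* A reader might infer that 100% is forced there too. The documents do not support this unless location status is a composite of all cores.
- *Reason codes.* A reader might infer that a concordant target, having no code, is lost to the DSS. C.3 does not score by reason code. It credits findings by match in sextant and zone, with review of ambiguous cases. The missing code is a record-keeping gap that matters once cores are attributed to methods.
- *Whose precision.* C.4 may look as if it describes an unspecified method. It lists the Gleason correlation beside the AUC, and C.3 ties that correlation to DSS output, so the figures read as the tool's. What is missing is the radiologist's value.
- *Loss of precision.* Setting 0.06 to 0.09 against C.4's ±0.03 suggests a two- to threefold loss. That misleads, because C.4's interval is about one SE. Against the single-method 95% half-width of 0.065, the paired half-width runs from slightly narrower to moderately wider.
- *Pairing.* C.3 names the comparison and AUC, both methods are applied to the same patients, and a paired analysis is not excluded. The second part therefore asks for something to be stated; it does not correct an error.

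**Conclusion.** The first part is wrong as written, on a subsidiary comparison. Per patient and at a common threshold, sextant specificity and PPV are exactly 100% by construction and carry no information. This is a matter of definition and needs no assumed figures. Sensitivity and NPV remain estimable but only relative to the composite of all cores.

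A reader might infer that the main result is biased as well. This point does not show that: the DSS tool and the radiologist are judged against the same reference, and the sextant scoring does not enter their contrast.

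The second part is an inexpensive improvement. The major goal has no stated estimate and no stated precision. The illustrative half-width of 0.06 to 0.09 rests on the assumed radiologist AUC and correlation, on C.4's 35% and on the per-patient analysis. The sponsor's own inputs should replace these.

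**What to change.** **C.3, sextant biopsy.** Drop specificity, PPV and AUC for this method. Report its detection rate of clinically significant cancer among all biopsied patients, paired within patient with radiologist-targeted and DSS-targeted detection. State beside it that the reference is the composite of all cores and that, under C.1, the radiologist decides which targets are biopsied, so DSS-targeted detection is not independent of the radiologist.

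**C.1, core labels.** Add a reason code for targets chosen by both methods, because the detection analysis attributes cores to methods.

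**C.3, main comparison.** Make the paired AUC difference, DSS minus radiologist, with a 95% CI the primary analysis. Use DeLong per patient, and a patient-clustered ROC method or patient-level bootstrap per location. Use the radiologist's graded suspicion score from the clinical read, fixed before the DSS output is seen.

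**C.4.** State the expected half-width of that difference under the sponsor's own AUCs, correlation and number of positives.

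**Cost.** A paragraph in C.3, a line in C.4 and one code, with a little more analysis work. No extra patients, scans or cores. The graded score may already be among the imaging results collected under section H; if so, only its timing needs fixing. The stated precision will look less favourable than the interval now printed in C.4.
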